#### **8.2.2 Control Intervention**

The control group will not undergo the pudendal nerve block.

#### **8.3 Dose / Device modifications**

No dose modification are planned

#### **8.4 Data Collection and Follow-up for withdrawn participants**

Results will be collected on specific printed formularies (CRFs). The Principal Investigator will preserve the sensitive data in his office in a closed cabinet key. Results will be then collected on a Redcap® electronic database. The access to the database will require username and password. Only the authorized personnel (physicians responsible for the study) will have the access rights and all changes on the database are trackable.

[figure not shown]
In-patients will be then controlled after 1 months and out-patients will be controlled after 1 and 4 weeks.

#### **8.5 Concomitant Interventions (treatments)**

No specific or relevant concomitant care or treatment are allowed.

## 9. STUDY ASSESSMENTS

### 9.1 Study flow chart(s) / table of study procedures and assessments

## 9.2 Assessments of outcomes

### 9.2.1 Assessment of primary outcome

Postoperative pain measured on VAS scale at 6, 12, 24, 48 hours. The data will be registered by the nursing personnel in the postoperative period on printed formularies (CRFs) or by the patient itself on a specific formulary.

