Measurements and procedures:	
Patients' clinical data and operative time will be collected
 
Patients selected will be randomized in two groups.
 
 
• Group A will undergo Milligan-Morgan hemorrhoidectomy under pudendal nerve block plus spinal anaesthesia
 
• Group B will undergo Milligan-Morgan hemorrhoidectomy under spinal anaesthesia
 
 
The randomization list will be created by the CTU-EOC and the randomization will be performed by the authorized personnel (physician responsible for the study, the anaesthetist and the surgeons) of the participating centre via RedCap®. Only the physician responsible for the study, the anaesthetist and the surgeons will be informed about the treatment arm.

	
After the operation all the patient will receive Metronidazole 500 mg x3 + Paracetamol 1 gr x4 + NSAID + opioids as needed for at least 48 hours. The postoperative pain will be evaluated at 6, 12, 24, 48 hours with VAS scale both as in-patients or out-patients on specific formularies. In-patients will be then controlled after 1 months, while out-patients after 1 and 4 weeks.
 
Results will be collected on specific printed Case report form. The Principal Investigator will preserve the sensitive data in his office in a closed cabinet key. Results will be then collected on a Redcap® electronic database. The access to the database will require username and password. Only the authorized personnel (physicians responsible for the study) will have the access rights and all changes on the database are trackable.

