### **11.3 Planned Analyses**

Descriptive statistics will be presented as mean with standard deviation (SD) or as median with interquartile range (IQR) for quantitative data. Qualitative data will be presented as absolute numbers with percentages. Comparisons of postoperative pain measured on VAS scale at 6, 12 and 24 h after surgery between group A and group B will be performed with the non-parametric repeated measures analysis of variance (Friedman test). By statistically significant p-value, post-hoc tests will be performed taken into account the multiple comparisons. Qualitative data between groups of patients will be compared with the Chi-Square test, or the Fisher exact test as appropriate. By statistically significant result post-hoc comparisons were made with the appropriate critical level adjustment. Comparisons of quantitative data between groups will performed with the Student's t-test or with the Mann-Whitney test as appropriate. All tests will be conducted two-sided, and p-values < 0.05 will be considered statistically significant. Stata version 12.1 (StatCorp. LP, College Station, TX, USA) will be used for all statistical analysis.

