### **11.4 Handling of missing data and drop-outs**

In case of missing data, the patient will be dropped-out. 2 drop-outs each arm is planned

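### The 12 h VAS reading is the one most at risk of being missed at night, and section 11.4 would then drop the whole patient

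*Combined protocol and SAP*

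**What the plan says.** Sections 5.1 and 9.2.1 define the primary outcome as "Postoperative pain measured on VAS scale at 6, 12, 24, 48 hours". Section 9.2.1 has the score recorded "by the nursing personnel in the postoperative period on printed formularies (CRFs) or by the patient itself on a specific formulary", and the synopsis (Measurements and procedures) says that this happens "both as in-patients or out-patients on specific formularies". The protocol text gives no tolerance around each time, no operating hours and no instruction for a patient who is asleep when a reading is due.

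Section 11.3 compares "VAS scale at 6, 12 and 24 h after surgery between group A and group B" with a Friedman test, so 48 h belongs to the primary outcome but not to the stated comparison. Section 11.4 reads: "In case of missing data, the patient will be dropped-out. 2 drop-outs each arm is planned". Section 11.3.1, by contrast, counts every randomised participant in the analyses. Section 11.2 sets 18 per group for 80% power at a type I error of 0.05 and raises this to 20 for 10% drop-out.

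**The concern.** Of the four times, 12 h is the one that routinely reaches the night after a daytime operation. An out-patient has nobody assigned to prompt a night reading, and an in-patient may be asleep. Those values are therefore at risk of being missing.

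On its plain wording, section 11.4 turns one missing value into the loss of the patient. Valid 6 and 24 h scores that the planned comparison would use go with it, as does the 48 h score. With room for 2 losses per arm, the allowance could be used up by this cause alone.

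If comfortable patients are the likelier sleepers, and the block works at 12 h (section 3.2 credits it with up to 24 h), the losses would also be heavier in Group A and concentrated among low scores.

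**Working it through.** **1. The plan's own figure.** 18 / (1 - 0.10) = 20 per group, as stated, which leaves room for 2 losses per arm. The 18 cannot be rebuilt because no SD or control mean is given. Solved backwards (two-sided 0.05, power 0.80), the standardised difference is d = (1.960 + 0.842) x sqrt(2/18) = 0.934, or 0.961 with the t distribution.

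**2. Share of 12 h readings at night.** Assume that surgery ends uniformly between a and b, and that night is 23:00-06:00. A 12 h reading falls at night if surgery ended between 11:00 and 18:00, so the share is the overlap of [a, b] with [11, 18], divided by b - a.

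| End of surgery (assumed) | Share at night |
|---|---|
| 08:00-12:00 | 1/4 = 25% |
| 08:00-14:00 | 3/6 = 50% |
| 08:00-16:00 | 5/8 = 62.5% |
| 09:00-17:00 | 6/8 = 75% |

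Other definitions of night and other lists give 0% to 87%. In every case tested the 24 and 48 h readings fall in the daytime; the 6 h reading falls at night in 0-20%.

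**3. When the allowance is used up.** Break-even is 0.10 divided by the night share: 40% of night readings missed at a 25% share, 20% at 50%, 16% at 62.5% and 13% at 75%.

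**4. Power after whole-patient deletion.** Power = Phi(0.934 x sqrt(n/2) - 1.96), with a 50% night share.

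| Night readings missed | Left per arm | Power | Chance an arm of 20 loses more than 2 |
|---|---|---|---|
| none | 20 | 84% | - |
| 20% | 18 | 80% | 32% |
| 50% | 15 | 72% | 91% |
| 100% | 10 | 53-55% | 100% |

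**5. Illustrative simulation with losses that depend on pain.** Assumptions: control mean 5 on a 0-10 scale, a 33% reduction (5 x 0.33 = 1.65), SD 1.65/0.961 = 1.72, within-patient correlation 0.5, and a 62.5% night share. The chance of missing a night reading is logistic in the 12 h score. Power is for an unadjusted t-test on the 6 h reading, 20 per arm before losses. Ranges cover two runs.

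| Scenario | Mean loss A / B | Power |
|---|---|---|
| Half the patients exposed; miss probability 0.5 at VAS 2, 0.1 at VAS 6 | 2.2 / 1.2 | 84% to 79-80% |
| All exposed; same probabilities | 4.3 / 2.5 | 84-85% to 74-75% |
| All exposed; 0.7 at VAS 2 | 5.8 / 3.1 | 84-86% to 70-72% |

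Attenuation at 12 h is 5% in the second row and 7% in the third. With all exposed and the first set of probabilities, a 50% night share gives losses of 3.4 and 2.0 and power of 76%; a 25% share gives 1.7 and 1.0, and 81%.

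**6. Bias check.** A separate simulation (correlation 0.6, 50% night share, sleep likelier with low pain, true difference 0.95 SD) deleted 18% of controls and 32% of block patients. The difference shrank to 0.91-0.93 SD. With no true effect there was no bias, so this mechanism does not create false positives.

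**The case against.** Several stronger readings are tempting, and the documents do not support them.

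- **Half or more of the 12 h readings fall at night.** Operating hours are not given, and a morning-only list gives 25% or less under a late definition of night.
- **A sleeping patient has no score.** A nurse may obtain one, or a form may be completed late. The patient form and the out-patient protocol listed in section 17, and the content of the 9.1 flow chart, are not in the text and may hold timing instructions. The reading is at risk, not certainly absent.
- **The patient is certainly deleted.** Section 11.3.1 says otherwise. The conflict does not rescue the plan, however: a standard Friedman test needs a complete row, so a missing 12 h value would still exclude the patient.
- **The trial will understate the block's benefit.** This needs sleep to mean low pain. Section 8.1.2 allows strong opioids as needed, so a patient may sleep because of sedation after severe pain, possibly more often in Group B. The direction is open.

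The power figures are also fragile. The larger drops require every patient to be exposed, although nurses record some scores. The miss probabilities have no source, and the test simulated is not the planned one. The 84% start is power with no losses, against a target of 80%; with half the patients exposed, the plan ends close to its target. Section 6.1 mentions 100 patients. At 50 per arm with 25% lost, 37.5 remain and power is Phi(0.934 x sqrt(37.5/2) - 1.96) = Phi(2.08), about 98%.

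What survives is the stated rule: one missed reading costs a patient whose other readings are valid, and the schedule has a foreseeable weak point.

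**Conclusion.** The point holds as a risk created by the plan's own wording. The 12 h value is the most exposed to the night, no window or sleep rule appears in the protocol text, and section 11.4, unreconciled with 11.3.1, would remove the whole patient. The main cost is lost patients. With 20 per arm, power falls from about 84% to about 79% with half the patients exposed and to about 70-75% with all exposed. These figures rest on assumed operating hours and miss probabilities, and on whole-patient deletion; without deletion all 20 per arm stay in, at 84%.

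Bias is secondary: about 5-7% attenuation at 12 h, conditional on sleep being commoner with low pain. A reader might infer serious bias, or a cost to the planned comparison from losing the 48 h score. Neither follows, because the simulated bias is small and 48 h is not in that comparison.

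**What to change.** 1. Reconcile 11.4 with 11.3.1: state that a missed VAS reading does not remove the patient and that all randomised patients are analysed with all their available readings.
2. Replace the Friedman test with a repeated-measures method that compares the arms and tolerates missing time points, for example a mixed model. If absence depends on the unseen 12 h score itself, some bias can remain.
3. On both forms, record the clock time of end of surgery and of each VAS reading, and note sleep as the reason for a missed 12 h value.
4. Analyse a score taken on waking at its actual time; do not relabel it as 12 h. For surgery ending at 14:00, waking at 06:00-07:00 is 16-17 h. A tolerance alone would not solve this: 2 h either way gives 00:00-04:00 in that example, and under the 08:00-16:00 assumption the earliest permitted reading is still at or after 23:00 for ends from 13:00 to 16:00 (3/8 = 37.5%).
5. Ranking sleepers as having the lowest pain is at most an optional sensitivity analysis, with its assumption stated.

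The cost is two extra form fields, a few sentences in 9.2.1, 11.3 and 11.4, and slightly more analysis work, with no added visit.

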### **9.2.2 Assessment of secondary outcomes**

Opioids drugs as needed, length of hospital stay and complications data will be registered by the care providers in the postoperative period on specific printed formularies.

### **9.2.3 Assessment of safety outcomes**

The type and the severity of AEs related to the pudendal nerve block will be recorded according to CTCAE Version 4.03 - June 14, 2010^12. The evaluation will be done after the nerve block, during the hospital stay and 1 months (in-patients) or 1 and 4 weeks (out-patients) after the operation.

#### **9.2.3.1 Adverse events**

For adverse event the information collected are: time of onset, duration, resolution, action to be taken, assessment of intensity, relationship with study treatment. The evaluations will be done during the hospital stay and during the further planned clinical evaluations.

### **9.2.4 Assessments in participants who prematurely stop the study**

Participants can be withdrawn from the study prematurely in case of adverse events after the pudendal nerve block.

## **9.3 Procedures at each visit**

One pre-operative visit is planned: history taking, physical examination, anaesthesiologist evaluation will be assessed.

All patients will be then controlled (history taking and clinical examination) after 1 months or 1 and 4 weeks (in- or out patients respectively).

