## **6. STUDY DESIGN**

### **6.1 General study design and justification of design**

This study is a randomized control single blind trial.

Patient will be randomized: Group A will undergo the pudendal nerve block under ultrasonographic control with injection of 10 mls of ropivacaine 0.75% before the spinal anaesthesia.

The population include patients with haemorrhoids (grade III and IV)

The study is single blind: an expert from the anaesthesiology team will perform the nerve block, the surgeon will be informed about the group of randomization. The nursing personnel (blinded) or the patient itself on specific formularies will evaluate the VAS scale at 6, 12, 24, 48 hours.

The comparator is no treatment

The method of randomization will be created by the CTU-EOC and the randomization will be performed by the authorized personnel (physician responsible for the study, the anaesthetist and the surgeons) of the participating centre via RedCap®. Only the physician responsible for the study, the anaesthetist and the surgeons will be informed about the treatment arm.

The expected duration of the study is 2 years, 100 patients.

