### **11.2 Determination of Sample Size**

Based on previous studies we will expect a 33% reduction in VAS scale. To detect a clinically relevant difference between groups with a type I error of 0.05 and a power of 0.80 we determined a sample size of 18 subjects per group. Taken into account a possible drop out for different reasons of 10% we calculated the definitive sample size in 20 patients per group.

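### The VAS comparison uses no covariates and no pre-operative VAS is scheduled, so precision that may be available from haemorrhoid grade and one baseline reading goes unused

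*Combined protocol and SAP*

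**What the plan says.** Section 5.1 sets the primary outcome as VAS at 6, 12, 24 and 48 hours. Section 9.2.1 repeats those four times, and so does the source-data list in section 12.1.2. None of them includes a reading before surgery. Section 9.3 describes the visit at which one could be taken: "One pre-operative visit is planned: history taking, physical examination, anaesthesiologist evaluation will be assessed".

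Section 11.3 covers "Comparisons of postoperative pain measured on VAS scale at 6, 12 and 24 h after surgery between group A and group B" and assigns this comparison to the Friedman test. The other comparisons use chi-square or Fisher, and Student's t or Mann-Whitney. No covariate, stratification factor or adjusted model is named there or in the synopsis.

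Patient information is nonetheless available before allocation. Section 7.1 makes grade III or IV an entry criterion, so each patient's grade has to be established at screening. The synopsis adds that patients' "clinical data and operative time will be collected".

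Sections 6.1, 6.2.1 and 7.3 say that the CTU-EOC creates the randomisation list and that it is run through REDCap. They do not describe how the list is built.

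**The concern.** In a trial of about 20 patients per arm, differences between patients that the treatment does not explain go straight into the standard error. A variable fixed before allocation that predicts postoperative VAS can remove part of that variation without adding a patient. The plan has one candidate at no cost (grade) and could have a second for one extra mark on a form (pre-operative VAS).

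Two features make the timing matter. A pre-operative VAS that is not taken before surgery cannot be recovered afterwards. And if the arms turn out visibly unequal in severity, an adjustment that was not pre-specified is open to the criticism that it was chosen after seeing the data.

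Operative time is also collected but is not a candidate. It is measured after allocation, so it should not be an adjustment variable.

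**Working it through.** **Inputs from the documents**

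- Section 11.2: the calculation is made "with a type I error of 0.05 and a power of 0.80", giving 18 per group, or 20 per group after 10% drop-out.
- Section 11.3: "All tests will be conducted two-sided".
- Section 11.2, effect: "Based on previous studies we will expect a 33% reduction in VAS scale". No control mean, SD or time point is given.

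**Inputs that must be assumed**

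- The correlation r between the covariate(s) and postoperative VAS. With two covariates, r is the multiple correlation.
- The number of grade IV patients.

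**1. The plan's own figures.** The drop-out step reproduces: 18 / (1 − 0.10) = 20. The 18 itself cannot be rebuilt, because a 33% relative reduction gives no sample size without a mean and an SD. Working backwards, a two-sided two-sample t-test with 18 per arm has 80% power at a standardised difference d = 0.961. That d is used below, so the 80% is nominal.

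**2. Gain before any cost.** Adjustment multiplies the residual variance by (1 − r²), so 18 per arm acts like 18 / (1 − r²). For r = 0.3 this is 18 / 0.91 = 19.8, and for r = 0.5 it is 18 / 0.75 = 24.0.

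**3. Gain net of cost.** Fitting k covariates costs k degrees of freedom, and chance imbalance in the covariates inflates the variance by an expected 1 + k / (N − 3 − k). With N = 36:

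- k = 1: 1 + 1/32 = 1.031, df = 33
- k = 2: 1 + 2/31 = 1.065, df = 32

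The noncentrality is d / √[(1 − r²) × inflation × 2/18]. For r = 0.3 and k = 2 this is 0.961 / √(0.91 × 1.065 × 0.111) = 2.93, which gives 81% power.

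| Assumed r | Before cost | Net, one covariate | Net, two covariates |
|---|---|---|---|
| 0 | 80% | 79% | 77% |
| 0.1 | 80% | 79% | 78% |
| 0.2 | 82% | 80% | 79% |
| 0.3 | 84% | 82% | 81% |
| 0.4 | 86% | 85% | 84% |
| 0.5 | 90% | 89% | 88% |

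Break-even is near r = 0.2 with one covariate and near r = 0.25 with two. The table models one VAS value per patient and a t-type comparison. It does not model the Friedman test.

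**4. Chance imbalance in grade.** Suppose 40 patients are allocated 20/20 without stratification and K of them are grade IV. The number of grade IV patients in one arm is then hypergeometric (40, K, 20). For K = 12, 16 and 20:

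- the arms differ by at least 4 grade IV patients with probability 0.301, 0.333 and 0.343
- they differ by at least 6 with probability 0.082, 0.105 and 0.113

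**5. Which sample size.** Section 11.2 implies 2 × 20 = 40 patients, but section 6.1 says 100. At 50 per arm the inflation in step 3 would fall to 1 + 1/96 = 1.010 or 1 + 2/95 = 1.021, so the cost of adjusting would nearly vanish.

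**The case against.** The strongest objection is that the benefit is unknown and could be negative. No correlation is given. Grade has two levels within a population already restricted to III and IV. A pre-operative VAS measures pain from haemorrhoids, before there is a surgical wound. This stands, and it is why the table starts at r = 0 and charges the cost of the covariates.

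The second objection is that the planned primary test is the larger problem. The Friedman test ranks repeated conditions within patients. It does not compare two independent arms, and it accepts no covariates. This also stands. The change therefore replaces the primary model; a covariate cannot simply be added to the planned test. Since that model needs replacing anyway, naming covariates in it adds little work.

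Third, version 1.2 is dated 8.10.2018, while the synopsis planned the first participant for 01.01.2018. Some patients may already lack a pre-operative VAS, and section 11.4 drops patients with missing data. The documents do not say whether enrolment had begun, but the fix has to allow for it.

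A reader might also infer three stronger things that the documents do not support:

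- **That an unadjusted comparison is biased or invalid.** It is neither. A valid unadjusted test already allows for chance imbalance in its type I error, and nothing in the documents links a difference of 4 grade IV patients to a shift in VAS.
- **That the list certainly ignores grade.** No stratification factor is named, but the list's structure is not described.
- **That VAS varies widely between these patients.** No SD is reported.

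**Conclusion.** The point holds as a missed, inexpensive improvement. Section 11.3 uses no patient characteristic in the VAS comparison, the named test could not use one, and no pre-operative VAS is scheduled, although grade is known at entry and a pre-operative visit exists. It would go too far to say that the plan demonstrably gives up precision; it leaves unused precision that may be there.

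At 18 evaluable patients per arm and a nominal 80%, two covariates change power by between about −3 points (r = 0) and +8 points (r = 0.5). One covariate changes it by between about −1 and +9 points. These figures rest on assumed correlations, on the back-solved effect of 0.961, and on the sample size in section 11.2 and not the 100 patients in section 6.1. The point ranks below the choice of primary test and the missing mean and SD behind the 18 per group.

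**What to change.** 1. In section 9.3 and on the CRF, add one VAS at the pre-operative visit, on the same form as the postoperative readings.
2. In section 11.3, pre-specify the A-versus-B comparison as a mixed model or regression with arm, time, haemorrhoid grade and pre-operative VAS. State which contrast is primary and which time points enter, since section 5.1 includes 48 hours and section 11.3 does not. Keep the unadjusted between-arm comparison as a sensitivity analysis.
3. If patients are already enrolled without a pre-operative VAS, adjust for grade only or name a missing-covariate method. State that a missing covariate does not trigger the section 11.4 drop-out rule.
4. If the list can still be changed and is not already stratified, consider stratifying by grade in REDCap.
5. Reconcile 20 per arm (section 11.2) with 100 patients (section 6.1).

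The cost is one VAS mark per patient at a visit already planned, a rewritten paragraph for the primary model, one or two degrees of freedom, and ethics committee approval first if the amendment counts as substantial under section 2.10. No added visit or staff is needed.
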